14.2.3.2 Time to event variables

The protocol should state which of the following variables is used in that study.

14.2.3.2.1 Progression-free survival

[figure not shown]
Usually in all Oncology studies, patients are followed for tumor progression after discontinuation of study medication for reasons other than progression or death. If this is not used, e.g. in Phase I or II studies, this should be clearly stated in the protocol. Note that randomized trials (preferably blinded) are recommended where PFS is to be the primary endpoint.

Progression-free survival (PFS) is the time from date of randomization/start of treatment to the date of event defined as the first documented progression or death due to any cause. If a patient has not had an event, progression-free survival is censored at the date of last adequate tumor assessment.

14.2.3.2.2 Overall survival

All patients should be followed until death or until patient has had adequate follow-up time as specified in the protocol whichever comes first. The follow-up data should contain the date the patient was last seen alive / last known date patient alive, the date of death and the reason of death (“Study indication” or “Other”).

Overall survival (OS) is defined as the time from date of randomization/start of treatment to date of death due to any cause. If a patient is not known to have died, survival will be censored at the date of last known date patient alive.

14.2.3.2.3 Time to progression

Some studies might consider only death related to underlying cancer as an event which indicates progression. In this case the variable “Time to progression” might be used. TTP is defined as PFS except for death unrelated to underlying cancer.

Time to progression (TTP) is the time from date of randomization/start of treatment to the date of event defined as the first documented progression or death due to underlying cancer. If a patient has not had an event, time to progression is censored at the date of last adequate tumor assessment.

14.2.3.2.4 Time to treatment failure

This endpoint is often appropriate in studies of advanced disease where early discontinuation is typically related to intolerance of the study drug. In some protocols, time to treatment failure may be considered as a sensitivity analysis for time to progression. The list of discontinuation reasons to be considered or not as treatment failure may be adapted according to the specificities of the study or the disease.

Time to treatment failure (TTF) is the time from date of randomization/start of treatment to the earliest of date of progression, date of death due to any cause, or date of discontinuation due to reasons other than ‘Protocol violation’ or ‘Administrative problems’. The time to treatment failure for patients who did not experience treatment failure will be censored at last adequate tumor assessment.

14.2.3.2.5 Duration of response

The analysis of the following variables should be performed with much caution when restricted to responders since treatment bias could have been introduced. There have been reports where a treatment with a significantly higher response rate had a significantly shorter duration of response but where this probably primarily reflected selection bias which is explained as follows: It is postulated that there are two groups of patients: a good risk group and a poor risk group. Good risk patients tend to get into response readily (and relatively quickly) and tend to remain in response after they have a response. Poor risk patients tend to be difficult to achieve a response, may have a longer time to respond, and tend to relapse quickly when they do respond. Potent agents induce a response in both good risk and poor risk patients. Less potent agents induce a response mainly in good risk patients only. This is described in more detail by [Morgan \(1988\)](#).

It is recommended that an analysis of all patients (both responders and non-responders) be performed whether or not a “responders only” descriptive analysis is presented. An analysis of responders should only be performed to provide descriptive statistics and even then interpreted with caution by evaluating the results in the context of the observed response rates. If an inferential comparison between treatments is required this should only be performed on all patients (i.e. not restricting to “responders” only) using appropriate statistical methods such as the techniques described in [Ellis, et al \(2008\)](#). It should also be stated in the protocol if duration of response is to be calculated in addition for unconfirmed response.

For summary statistics on “responders” only the following definitions are appropriate. (Specific definitions for an all-patient analysis of these endpoints are not appropriate since the status of patients throughout the study is usually taken into account in the analysis).

Duration of overall response (CR or PR): For patients with a CR or PR (which may have to be confirmed) the start date is the date of first documented response (CR or PR) and the end date and censoring is defined the same as that for time to progression.

The following two durations might be calculated in addition for a large Phase III study in which a reasonable number of responders is seen.

Duration of overall complete response (CR): For patients with a CR (which may have to be confirmed) the start date is the date of first documented CR and the end date and censoring is defined the same as that for time to progression.

Duration of stable disease (CR/PR/SD): For patients with a CR or PR (which may have to be confirmed) or SD the start and end date as well as censoring is defined the same as that for time to progression.

14.2.3.2.6 Time to response

Time to overall response (CR or PR) is the time between date of randomization/start of treatment until first documented response (CR or PR). The response may need to be confirmed depending on the type of study and its importance. Where the response needs to be confirmed then time to response is the time to the first CR or PR observed.

Although an analysis on the full population is preferred a descriptive analysis may be performed on the “responders” subset only, in which case the results should be interpreted with caution and in the context of the overall response rates, since the same kind of selection bias may be introduced as described for duration of response in [Section 14.2.3.2.5](#). It is recommended that an analysis of all patients (both responders and non-responders) be performed whether or not a “responders only” descriptive analysis is presented. Where an inferential statistical comparison is required, then all patients should definitely be included in the analysis to ensure the statistical test is valid. For analysis including all patients, patients who did not achieve a response (which may have to be a confirmed response) will be censored using one of the following options.

- at maximum follow-up (i.e. FPFV to LPLV used for the analysis) for patients who had a PFS event (i.e. progressed or died due to any cause). In this case the PFS event is the worst possible outcome as it means the patient cannot subsequently respond. Since the statistical analysis usually makes use of the ranking of times to response it is sufficient to assign the worst possible censoring time which could be observed in the study which is equal to the maximum follow-up time (i.e. time from FPFV to LPLV)
- at last adequate tumor assessment date otherwise. In this case patients have not yet progressed so they theoretically still have a chance of responding

Time to overall complete response (CR) is the time between dates of randomization/start of treatment until first documented CR. Similar analysis considerations including (if appropriate) censoring rules apply for this endpoint described for the time to overall response endpoint.

14.2.3.2.7 Definition of start and end dates for time to event variables

Assessment date

For each assessment (i.e. evaluation number), the **assessment date** is calculated as the latest of all measurement dates (e.g. X-ray, CT-scan) if the overall lesion response at that assessment is CR/PR/SD/UNK. Otherwise - if overall lesion response is progression - the assessment date is calculated as the earliest date of all measurement dates at that evaluation number.

Start dates

For all “time to event” variables, other than duration of response, the randomization/ date of treatment start will be used as the start date.

For the calculation of duration of response the following start date should be used:

- Date of first documented response is the assessment date of the first overall lesion response of CR (for duration of overall complete response) or CR / PR (for duration of overall response) respectively, when this status is later confirmed.

End dates

The end dates which are used to calculate ‘time to event’ variables are defined as follows:

- Date of death (during treatment as recorded on the treatment completion page or during follow-up as recorded on the study evaluation completion page or the survival follow-up page).
- Date of progression is the first assessment date at which the overall lesion response was recorded as progressive disease.
- Date of last adequate tumor assessment is the date the last tumor assessment with overall lesion response of CR, PR or SD which was made before an event or a censoring reason occurred. In this case the last tumor evaluation date at that assessment is used. If no post-baseline assessments are available (before an event or a censoring reason occurred) the date of randomization/start of treatment is used.
- Date of next scheduled assessment is the date of the last adequate tumor assessment plus the protocol specified time interval for assessments. This date may be used if back-dating is considered when the event occurred beyond the acceptable time window for the next tumor assessment as per protocol (see [Section 14.2.3.2.8](#)).

Example (if protocol defined schedule of assessments is 3 months): tumor assessments at baseline - 3 months - 6 months - missing - missing - PD. Date of next scheduled assessment would then correspond to 9 months.

- Date of discontinuation is the date of the end of treatment visit.
- Date of last contact is defined as the last date the patient was known to be alive. This corresponds to the latest date for either the visit date, lab sample date or tumor assessment date. If available, the last known date patient alive from the survival follow-up page is used. If no survival follow-up is available, the date of discontinuation is used as last contact date.

- Date of secondary anti-cancer therapy is defined as the start date of any additional (secondary) antineoplastic therapy or surgery.

14.2.3.2.8 Handling of patients with non-measurable disease only at baseline

It is possible that patients with only non-measurable disease present at baseline are entered into the study, either because of a protocol violation or by design (e.g. in Phase III studies with PFS as the primary endpoint). In such cases the handling of the response data requires special consideration with respect to inclusion in any analysis of endpoints based on the overall response evaluations.

It is recommended that any patients with only non-measurable disease at baseline should be included in the main (ITT) analysis of each of these endpoints.

Although the text of the definitions described in the previous sections primarily relates to patients with measurable disease at baseline, patients without measurable disease should also be incorporated in an appropriate manner. The overall response for patients with measurable disease is derived slightly differently according to Table 14-8.

Table 14-8 Overall lesion response at each assessment: patients with non-target disease only

Non-target lesions	New Lesions	Overall lesion response
CR	No	CR
Non-CR/Non-PD ¹	No	Non-CR/non-PD
UNK	No	UNK
PD	Yes or No	PD
Any	Yes	PD

[figure not shown]
¹ As defined in [Section 14.2.2.4](#).

[figure not shown]
In general, the **non-CR/non-PD response** for these patients is considered equivalent to an SD response in endpoint determination. In summary tables for best overall response patients with only non-measurable disease may be highlighted in an appropriate fashion e.g. in particular by displaying the specific numbers with the non-CR/non-PD category.

In considering how to incorporate data from these patients into the analysis the importance to each endpoint of being able to identify a PR and/or to determine the occurrence and timing of progression needs to be taken into account.

For ORR it is recommended that the main (ITT) analysis includes data from patients with only non-measurable disease at baseline, handling patients with a best response of CR as “responders” with respect to ORR and all other patients as “non-responders”.

For PFS, it is again recommended that the main ITT analyses on these endpoints include all patients with only non-measurable disease at baseline, with possible sensitivity analyses which exclude these particular patients. Endpoints such as PFS which are reliant on the determination and/or timing of progression can incorporate data from patients with only non-measurable disease.

14.2.4 Data handling and programming rules

The following section should be used as guidance for development of the protocol, data handling procedures or programming requirements (e.g. on incomplete dates).

14.2.4.1 Study/project specific decisions

For each study (or project) various issues need to be addressed and specified in the protocol or RAP documentation. Any deviations from protocol must be discussed and defined at the latest in the RAP documentation.

The proposed primary analysis and potential sensitivity analyses should be discussed and agreed with the health authorities and documented in the protocol (or at the latest in the RAP documentation before database lock).

14.2.4.2 End of treatment phase completion

Patients **may** voluntarily withdraw from the study treatment or may be taken off the study treatment at the discretion of the investigator at any time. For patients who are lost to follow-up, the investigator or designee should show "due diligence" by documenting in the source documents steps taken to contact the patient, e.g., dates of telephone calls, registered letters, etc.

The end of treatment visit and its associated assessments should occur within 7 days of the last study treatment.

Patients may discontinue study treatment for any of the following reasons:

- Adverse event(s)
- Lost to follow-up
- Physician decision
- Pregnancy
- Protocol deviation
- Technical problems
- Subject/guardian decision
- Death
- Progressive disease
- Study terminated by the sponsor
- Non-compliant with study treatment
- No longer requires treatment
- Treatment duration completed as per protocol (optional, to be used if only a fixed number of cycles is given)

14.2.4.3 End of post-treatment follow-up (study phase completion)

End of post-treatment follow-up visit will be completed after discontinuation of study treatment and post-treatment evaluations but prior to collecting survival follow-up.

Patients may provide study phase completion information for one of the following reasons:

- Adverse event
- Lost to follow-up
- Physician decision
- Pregnancy
- Protocol deviation
- Technical problems
- Subject/guardian decision

- Death
- New therapy for study indication
- Progressive disease
- Study terminated by the sponsor

14.2.4.4 Medical validation of programmed overall lesion response

As RECIST is very strict regarding measurement methods (i.e. any assessment with more or less sensitive method than the one used to assess the lesion at baseline is considered UNK) and not available evaluations (i.e. if any target or non-target lesion was not evaluated the whole overall lesion response is UNK unless remaining lesions qualified for PD), these UNK assessments may be re-evaluated by clinicians at Novartis or external experts. In addition, data review reports will be available to identify assessments for which the investigators' or central reader's opinion does not match the programmed calculated response based on RECIST criteria. This may be queried for clarification. However, the investigator or central reader's response assessment will never be overruled.

If Novartis elect to invalidate an overall lesion response as evaluated by the investigator or central reader upon internal or external review of the data, the calculated overall lesion response at that specific assessment is to be kept in a dataset. This must be clearly documented in the RAP documentation and agreed before database lock. This dataset should be created and stored as part of the 'raw' data.

Any discontinuation due to 'Disease progression' without documentation of progression by RECIST criteria should be carefully reviewed. Only patients with documented deterioration of symptoms indicative of progression of disease should have this reason for discontinuation of treatment or study evaluation.

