7.1.7.2 Post-Treatment Follow-up

All patients who discontinued treatment during the treatment phase for reasons other than death, lost to follow-up, pregnancy or disease progression as per investigator assessment (Section 7.1.3) will continue tumor and [REDACTED] as per Table 7-1 (every 8 weeks) thereafter until PD as per investigator assessment, withdrawal of consent or death. Once the patient ceases tumor follow-up, the reason for completion should be recorded on the End of Post Treatment Disposition (Study Phase Completion) eCRF page.

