Tumor assessments will be done until RECIST-defined PD by investigator assessment, death, lost to follow-up, or patient decision involving withdrawal of consent.

If a patient discontinues study treatment in the absence of PD, tumor assessments will continue to be done every 8 weeks until RECIST-defined PD by investigator assessment, death, lost to follow-up, or patient decision involving withdrawal of consent.

If a patient continues treatment with LDK378 after RECIST-defined PD by investigator assessment, no further imaging assessments on study are required.

Imaging evaluations will also be performed at the End of Treatment (EOT) visit. If a patient is known to have PD at a scheduled study visit, EOT imaging evaluations do not need to be repeated for the EOT visit.

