3.2.10.2 Other secondary efficacy objectives

The other secondary efficacy objectives are:

- To evaluate DOR, DCR, TTR, OIRR and PFS both by investigator assessment and BIRC assessment
- To evaluate ORR and OIRR by BIRC
- To evaluate OS

Duration of Response

Among patients with a confirmed response (PR or CR) per RECIST 1.1 by investigator, DOR is defined as the time from first documented response (PR or CR) to the date of first documented disease progression or death due to any cause. If a patient has not had an event, DOR is censored at the date of last adequate tumor assessment.

The censoring and event date options to be considered for the DOR analysis follow those for PFS below.

DOR will be described in tabular and graphical format using Kaplan-Meier methods including estimated median (in months) with 95% CI, 25th and 75th percentiles ([Brookmeyer and Crowley 1982](#), [Klein and Moeschberger 1997](#)) and Kaplan-Meier estimated probabilities with corresponding 95% CIs ([Kalbfleisch and Prentice 1980](#)) at several time points (including at least 3, 6, 9, 12, 15 and 18 months).

Refer to [Section 4.2.3.3](#) for further details regarding derivation of Kaplan –Meier estimates.

Disease control rate

DCR, defined as the proportion of patients with best overall response of CR, PR, SD, or Non-CR/Non-PD per RECIST 1.1 by investigator will be estimated and the 95% CI ([Clopper & Pearson, 1934](#)) based on the exact binomial distribution will be provided.

Time to response

Time to overall response of CR or PR (TTR) is defined as the time from start of study drug to first documented response (CR or PR, which must be confirmed subsequently) for patients with a confirmed CR or PR.

TTR will be summarized in 2-month intervals using descriptive statistics. The analysis will be performed based on investigator assessment.

Progression-free survival

PFS is defined as the time from the date of first dose of study drug to the date of the first documented disease progression per RECIST 1.1 by investigator, or death due to any cause.

If a patient has not progressed or is not known to have died at the date of analysis cut-off or has received any anticancer therapy other than study drug, PFS will be censored at the date of the last adequate tumor evaluation before the cut-off date or before the start of the new anticancer therapy date, whichever is earlier. Clinical deterioration will not be considered as a qualifying

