event for progression. Refer to [Table 3-3](#) for censoring and event date options and outcomes for PFS.

In particular, PFS will be censored at the last adequate tumor assessment if one of the following occurs: absence of event; the event occurred after a new anticancer therapy is given; the event occurred after two or more missing tumor assessments (see [Section 4.2.1](#)). See also [Section 4.2.1](#) describing the special case of a missing baseline tumor assessment.

PFS will be described in tabular and graphical format using Kaplan-Meier methods as described for DOR, including estimated median (in months) with 95% CI, 25th and 75th percentiles and Kaplan-Meier estimated probabilities with corresponding 95% CIs at several time points (including at least 3, 6, 12, 18 and 24 months). Censoring reasons will also be summarized (see [Section 4.2.1](#))

Table 3-4 Outcome and event dates for PFS and DOR analyses

Situation	Date	Outcome
A No baseline assessment	Date of first dose of study drug ^a	Censored
B Progression at or before next scheduled Assessment	Date of progression	Progressed
C1 Progression or death after exactly one missing assessment	Date of progression (or death)	Progressed
C2 Progression or death after two or more missing assessments	Date of last adequate assessment	Censored
D No progression	Date of last adequate assessment	Censored
E Treatment discontinuation due to 'Disease progression' without documented progression, i.e. clinical progression based on investigator claim	N/A	Information ignored. Outcome derived based on radiology data only.
F New anticancer therapy given	Date of last adequate assessment	Censored

^aThe rare exception to this is if the patient dies no later than the time of the second scheduled assessment as defined in the protocol in which case this is a PFS event at the date of death

In addition, summary tables of PFS by brain metastasis at baseline status (presence vs. absence) will be generated by investigator and BIRC assessment respectively.

Overall survival

OS is defined as the time from the first dose of study drug to the date of death due to any cause. If the patient is alive at the date of the analysis cut-off or lost to follow-up, then OS will be censored at the last contact date prior to data cutoff date (see [Section 4.1.4](#) for further details on derivation of last contact date).

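### Symptomatic progression without RECIST documentation may end tumour evaluation on some protocol wording, yet the SAP never counts it as an event, so PFS and DOR could be censored informatively and no planned analysis would show it

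*Protocol*

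**What the plan says.** **When scanning stops.** Protocol 7.2.1.2 says that after treatment ends without PD, "tumor assessments will continue to be done every 8 weeks until RECIST-defined PD by investigator assessment"; the other listed stops are death, loss to follow-up and withdrawal of consent. Section 4.1 agrees, and SAP 2.4 has the same schedule.

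Three places are looser:
- Protocol 7.1.7.2 exempts from further scans patients who stopped for "pregnancy or disease progression as per investigator assessment" and does not mention RECIST.
- Protocol 6.1.3 exempts disease progression from efficacy follow-up, with no qualifier in that sentence.
- Protocol 14.2.4.4, on discontinuations for progression without RECIST documentation, asks for careful review and then states: "Only patients with documented deterioration of symptoms indicative of progression of disease should have this reason for discontinuation of treatment or study evaluation".

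**What counts as an event.** SAP Table 3-4 row E covers "Treatment discontinuation due to 'Disease progression' without documented progression, i.e. clinical progression based on investigator claim". Its outcome is "Information ignored. Outcome derived based on radiology data only". The PFS text agrees: "Clinical deterioration will not be considered as a qualifying" event for progression. SAP 4.2.1 applies this to every efficacy endpoint.

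**Where the patient is then censored.** "PFS will be censored at the last adequate tumor assessment if one of the following occurs: absence of event". Row F censors at the same point once new anticancer therapy is given. For DOR, "The censoring and event date options to be considered for the DOR analysis follow those for PFS below".

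**The concern.** The looser passages let a broad notion of progression end the search for an event, while the SAP accepts only a narrow one as the event. A patient who deteriorates clinically can fall between the two, with no further scans and no progression recorded. Such a patient is censored because the disease is getting worse. Kaplan-Meier estimation treats that patient's later course as like that of patients still under observation, so the error runs upward.

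The trial has a single arm and is meant to support registration in China (Protocol 2.1, 2.2). Protocol 2.2 uses DOR to supplement ORR and calls PFS an important supportive endpoint. There is no control arm in which the same bias would also appear. ORR, the sample size and the PK and safety objectives are not affected.

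**Working it through.** **1. The plan's own threshold.** SAP 4.2.1 sets D2 = 2 × 8 weeks + 2-week window = 18 weeks, which reproduces. A death or RECIST PD within 18 weeks of the last adequate scan still counts, unless new therapy came first.

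**2. Possible paths after symptomatic progression without RECIST PD.**

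| Path | Result under the SAP |
|---|---|
| Scans continue to RECIST PD, no new therapy | Event at RECIST PD |
| End-of-treatment (EOT) scan shows PD | Event |
| Scans stop, death within 18 weeks, no new therapy | Event at death |
| Scans stop, no death within 18 weeks | Censored at last adequate scan |
| New therapy before RECIST PD, scans continued or not | Censored at last adequate scan (row F) |

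Only the last two paths cause the problem. Continued scanning closes the fourth but not the fifth.

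**3. Size, as an illustration.**

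Inputs from the documents:
- median PFS 6.90 months after a prior ALK inhibitor, from the earlier study (Protocol 1.2.1.2.2)
- 103 treated patients (Protocol, amendment summary)
- scans every 8 weeks
- D2 = 18 weeks = 126 days

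Assumptions, because the documents give no figure:
- share f of progressions that are clinical only: 5% to 15%
- exponential times, with mean survival after progression of 6 months
- follow-up of 6 to 18 months

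For a clinical-only patient, the plan's rule gives an event at death if death falls within 126 days of the last scan, and otherwise censors at that scan. The comparator is an event at clinical progression. With scanning stopped and no EOT scan showing PD, 6-month PFS is:

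| f | Clinical PD counted | Row E | Difference |
|---|---|---|---|
| 5% | 57.4% | 58.5% | +1.1 |
| 10% | 57.2% | 59.4% | +2.2 |
| 15% | 56.9% | 60.3% | +3.4 |

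The standard error of 6-month PFS with 103 patients is about √(0.574 × 0.426 / 103) = 0.049, or roughly 5 points.

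**4. Variations at f = 10%, 6-month PFS.**
- Half of EOT scans show PD (assumed): the difference falls from +2.2 to about +1.2. At 80% (assumed), it is about +0.5.
- No death is captured, for example because every such patient switches therapy: 57.2% against 60.1%, a difference of +2.9 (separate large-sample run, scans ±1 week).
- Scanning continues to RECIST PD without new therapy: 57.4% to 57.5% against 57.2%. The difference stays under 1 point even at f = 30% (57.5% against 56.7%).

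No median shift is quoted. With 8-weekly scans the curve falls in steps, so the median either stays put or jumps a whole step depending on small details of the set-up. No DOR shift is quoted either, because it would need further assumptions about when responses start relative to scans.

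**The case against.** The strongest case is that the protocol, read as a whole, already keeps these patients on scans. Section 7.2.1 uses 'investigator assessment' to mean the local RECIST 1.1 reading, as distinct from the independent review. Sections 6.1.3 (first bullet), 7.1.4 and 7.1.5 describe progression as radiological. Section 14.2.4.4 belongs to a generic cross-study appendix, calls for careful review, and restricts who may carry the progression code. Section 7.2.1.2 also requires imaging at the EOT visit, due within 7 days of the last dose, unless PD is already known. Radiology-only progression is prespecified, and PFS and DOR are descriptive; Protocol 10.10 says the study is not powered for formal testing. The SAP already tabulates reasons for treatment discontinuation, censoring reasons and follow-up gaps.

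Much of this stands. Continued scanning is the more natural reading, and a radiology-only rule is not biased in itself. A reader might infer that the plan does overstate PFS and DOR. The documents do not support that: 4.1 and 7.2.1.2 require scans to RECIST PD, EOT imaging will turn some of these patients into events, early deaths count, and no count of such patients is given.

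Three things remain. SAP 4.2 adopts Appendix 2 for this study, and 14.2.4.3 lists progressive disease, unqualified, as a reason for ending post-treatment follow-up, so a site has text to rely on. Row E exists because such patients are expected, yet none of the six PFS censoring reasons in SAP 4.2.1 identifies them. And continued scanning does not help a patient who switches therapy before RECIST PD.

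**Conclusion.** The passages conflict on what ends tumour assessment, and the SAP has no analysis showing how much that matters. The possible bias is upward for both PFS and DOR, but it is conditional: it arises only if sites stop scanning on the looser wording or if patients start new therapy before RECIST PD.

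Its size is unknown. On the assumed 5% to 15% share it is about 1 to 3 points on 6-month PFS when no EOT scan shows PD. That is below one standard error at each share, but it does not average out as sampling error does. It shrinks as EOT scans capture PD, and is close to zero if scanning runs on to RECIST PD without new therapy. The point warrants a wording correction and a sensitivity analysis. It does not support a claim that the reported PFS or DOR will be wrong.

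**What to change.** 1. Reconcile Protocol 6.1.3, 7.1.7.2 and 14.2.4.4 with 4.1 and 7.2.1.2, so that, on grounds of progression, only RECIST 1.1-documented progression ends tumour assessments.
2. In SAP 3.2.10.2, keep row E for the main analysis. Add a sensitivity analysis of PFS and DOR that counts discontinuation for 'Disease progression' without RECIST PD as an event on the discontinuation date. It should include patients who then start new therapy, whom row F would otherwise censor.
3. Tabulate the number of such patients, using the disposition page already collected.

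The cost is three wording changes, one extra analysis run and one count. The sensitivity estimate will be slightly less favourable. Recruitment is complete, so the protocol wording helps only patients still in tumour follow-up; the SAP additions apply to all treated patients.
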